7.2.1 Randomization

The participant to be eligible requires to present symptoms of trigeminal neuropathic pain for a minimum of 3 months (12 weeks). In addition, the participant to be eligible is required to have 80% compliance with the Daily Symptom Diary for the baseline period after visit 0 and reported an average pain intensity score of 4/10 in where 0= no pain and 10= maximum pain imaginable on a numerical rating scale (0-10), during the 4 weeks/28 days baseline period prior randomization as specified in the inclusion criteria. Participants then will be randomly assigned to one of two groups (Erenumab or placebo) and will be scheduled for Visit 1. Visit 1 should be scheduled within a week after randomization.

7.3 Treatment Visits

Visits 1-4

Participants will be receiving 3 cycles of either erenumab or placebo in visits 1-3. On visit 4, treatment will not be delivered but assessments will be performed.

7.3.1 First treatment cycle (Visit 1, Day 0)

- Review Daily Symptom Diaries in eCRF or collect and review it in paper forms
- Review medical/dental history to determine eligibility based on inclusion/exclusion criteria.
- Record concomitant medications and therapies
- Take blood pressure and collect weight
- Assess and record adverse events (AEs)
- Perform urine pregnancy test (in women of childbearing potential)
- Review 4 questionnaires from Visit 0 in eCRF or collect and review the paper forms

- Provide instruction to complete 4 new outcome measure questionnaires in paper or electronically for review at Visit 2.
- Provide instruction to complete Daily Symptom Diaries electronically or provide them in paper forms
- Deliver the injection of the study drug or placebo
- Schedule next visit

7.3.2 Visit 2, 2nd treatment/cycle (Day 28+/-3 days/ 4 weeks after Visit 1)

- Review Daily Symptom Diaries in eCRF or collect and review it in paper forms
- Assess compliance with Daily Symptom Diaries
- Review medical history
- Record concomitant medications and therapies
- Take blood pressure and collect weight
- Assess and record adverse events (AEs)
- Perform urine pregnancy test (in women of childbearing potential)
- Review 4 questionnaires from Visit 1 in eCRF or collect and review the paper forms
- Provide instruction to complete 4 new outcome measure questionnaires in paper or electronically for review at Visit 3.
- Provide instruction to complete Daily Symptom Diaries electronically or provide them in paper forms
- Deliver the injection of the study drug or placebo
- Schedule next visit

7.3.3 Visit 3, 3rd and final treatment cycle (Day 56+/- 3 days after 4 weeks from Visit 2)

Review Daily Symptom Diaries in eCRF or collect and review it in paper forms

- Assess compliance with Daily Symptom Diaries
- Review medical history
- Record concomitant medications and therapies
- Take blood pressure and collect weight
- Assess and record adverse events (AEs)
- Perform urine pregnancy test (in women of childbearing potential)
- Review 4 questionnaires from Visit 2 in eCRF or collect and review the paper forms
- Provide instruction to complete 4 new outcome measure questionnaires in paper or electronically for review at Visit 4.
- Provide instruction to complete Daily Symptom Diaries electronically or provide them in paper forms
- Deliver the injection of the study drug or placebo
- Schedule next visit

7.3.4 Visit 4, assessment of last treatment cycle (Day 84+/- 3 days,4 weeks after Visit 3

- Review Daily Symptom Diaries in eCRF or collect and review it in paper forms
- Assess compliance with Daily Symptom Diaries
- Review medical history
- Record concomitant medications and therapies
- Take blood pressure and collect weight
- Assess and record adverse events (AEs)
- Perform QST

- Perform EEG
- Collect blood for Cytokine release assay
- Perform urine pregnancy test (in women of childbearing potential)
- Review 4 questionnaires from Visit 3 in eCRF or collect and review the paper forms
- Provide instruction to complete 4 new outcome measure questionnaires in paper or electronically for review at Visit 5.
- Provide instruction to complete Daily Symptom Diaries electronically or provide them in paper forms
- Schedule next visit

7.4 Follow up and final Study Visit, Visit 5 (Day 112 +/- 3 days, 4 weeks after Visit 4)

- Review Daily Symptom Diaries in eCRF or collect and review it in paper forms
- Assess compliance with Daily Symptom Diaries
- Review 4 questionnaires from Visit 4 in eCRF or collect and review the paper forms
- Review medical history
- Record concomitant medications and therapies
- Take blood pressure and collect weight
- Assess and record adverse events (AEs)
- Perform urine pregnancy test (in women of childbearing potential)
- Provide final instructions to subject (in case of AE showing later)
- Complete a disposition form

7.5 Withdrawal Visit

An early termination visit will be performed if a participant is suspended before the completion of the study, prior to withdrawal of consent and with the participant's permission. This could happen during a scheduled or unscheduled visit. The investigator, study coordinator or research staff will discuss with the participant to contact the research team in case AE arise after the withdrawal visit. The assessment and procedures of Visit 4 will be conducted at this visit.

7.6 Unscheduled Visit

These visits may occur at the discretion of the investigator. Reasons may include but not limited: The need for withdrawal of the study; the participant is not able to attend a scheduled visit on a specific date; inability to collect the blood sample at the scheduled visit and in case of an Adverse Effect.

8 STUDY PROCEDURES /EVALUATIONS

8.1 Study Procedures/Evaluations

Medical History

The medical history will be taking by trained personnel during the interview and will be entered into the eCRF and will be updated each visit. As a part of the medical history, the study staff will administered a symptom inventory to assess/screen for possible AEs anticipated with the use of Erenumab throughout the study (V1-V5). Staff will record and evaluate new or worsened symptoms as possible AEs.

Medications and other therapies

Pharmacological therapies such as prescription and OTC medications and non-pharmacological therapies used in the last 30 days prior Visit 0 and during the course of the study will be recorded by trained personnel in the eCRF and will be updated in each visit.

Vital Signs and weight collection

After the medical history is taken, trained personnel will take the blood pressure and collect height and weight. Weight collection and blood pressure reading will be performed in each visit.

Pregnancy Test

Erenumab is not recommended to use during pregnancy, therefore female participants of childbearing potential will be screened for pregnancy with a urine test (instant type) that will be performed at every study visit. The results will be read by the study staff. The urine will be discarded after the test.

Blood Collection

A blood sample will be collected at Visits 0 and 4 by staff trained in phlebotomy. Blood samples will be evaluated then for the presence cytokines by Luminex assay.

Sensory Testing/QST

QST is a psychophysical procedure in which a test stimuli is applied at a defined intensity to a participant. The participant will report his/her perceptions of the intensity and the quality of the stimulus. We will be performing an extraoral QST [35-38].

General sensory testing:

Mechanical cutaneous pain sensitivity: Will be performed with weighted probes (2mm diameter; 8–512 mN forces) applied to the dorsum of digits 2, 3, and 4 of the left hand.

Thermal (heat) stimulation: Contact heat stimuli will be applied to the ventral forearm using a thermal probe temperature not exceeding 50 degrees Celsius.

Extraoral chair side QST: The cotton swab test will test sensitivity to non-painful mechanical stimulation (low-sensitivity). With the use of a cotton swab, the skin will be gently stroked 3-4 times with strokes of 1-2 cm in length in the area of V1, V2 and V3 and we will compare responses between the non-painful side to the painful side to detect normosensitivity, hyposensitivity, hypersensitivity and allodynia.

The spatula test will test temperature sensitivity following the same procedure as in the other 2 tests and temperature will be applied for 2-3 seconds. It is performed with a spatula that will be cold not exceeding 5 degrees Celsius or heated in a water bath until is 40 degrees Celsius.

EEG Assessment

EEG assessment will be performed in all participants. In chronic pain patients, alpha rhythms are slower in frequency and elevated in power relative to matched, healthy controls[39, 40]. Within the alpha band, the frequency at which maximum power is displayed, known as peak alpha frequency (PAF), varies considerably amongst individuals [45]. We have shown that PAF predicts future pain sensitivity in multiple experimental pain models [41-43]. We will examine whether erenumab can modulate PAF and therefore mediate clinical effects. PAF is based on a 5-minute, eyes-closed resting state EEG.

Daily Symptom Diary

Participants will be asked to complete the Daily Symptom Diary at the end of each day starting at the baseline phase and through the entire study (visits 1-5). Participants should have at least 80% compliance with the DSD the entire month, the equivalent of 23 completed days.

The diary collects the participant's pain intensity (reported on a 0-10 numeric rating scale) and use of pain medication. Participants are required to complete a Daily Symptom Diary electronically or on paper and a new form will be used for each month of the study. These forms may be returned in person at study visits.

Outcome Measure Questionnaires

Listed in the Schedule of Events (Appendix A). Questionnaire forms on paper will be provided to the participants if an electronic form is not feasible.

Some questionnaires are self-administered, and others will be administered by trained study staff.

- Penn Facial Pain Scale-Revised: Brief 12 item questionnaire (the higher the score the more pain and disability) to assess burden and restrictions of daily activities in patients with trigeminal neuralgia (e.g. chewing, eating, talking, touching) and assess and monitor the impact of treatment interventions [31].
- Graded Chronic Pain Scale (GCPS). The GCPS includes 7 items and assesses 2 dimensions of pain: pain intensity and pain-related disability [32].
- Patient Global Impression of Change (PGIC). This instrument measures change
 in participant's overall status on a scale ranging from 1 (very much improved) to 7
 (very much worse). The PGIC is based on the Clinical Global Impression of
 Change, which is a validated scale [33, 46].
- Hospital Anxiety and Depression Scale. Evaluates anxiety and depression with a 14-item instrument [34].

8.2 Laboratory Procedures/Evaluations

8.2.1 Clinical Laboratory Evaluations

 Pregnancy test: Female participants of childbearing potential will be screened for pregnancy with a urine test (instant type) that will be performed at every study visit.
 The results will be read by the study staff. The urine will be discarded after the test.

8.2.2 Special Assays or Procedures

Blood Collection to evaluate cytokine profile

- A blood sample will be collected at Visits 1 and 4 by staff trained in phlebotomy. Blood samples will be evaluated then for the presence of pro-inflammatory and anti-inflammatory cytokines by Luminex assay.
- Pre-collection preparation participants do not require any special preparation for the sample collection.
- Mode of collection A blood sample will be taken by a blood draw.
- Amount, frequency, and quality of specimen collection The blood sample will consist of 10-15 ml this will be for each subject and will be taking on visits 1 and 4
- Specimen collection duration We estimate that the collection procedure will have a duration of 15 minutes.

8.2.3 Specimen Preparation, Handling, and Storage

Collection of blood will be performed by trained staff in phlebotomy at the School of Dentistry and serum/plasma isolation and storage will be held at the same school. The samples will be labeled with the same unique identification number provided for the participant at the moment of enrollment in our study and randomization. Peripheral blood leukocytes (PBLs) and plasma will be isolated from 10-15 ml of the subjects' blood and stored at -80°C. The plasma fraction will be used for analysis of the presence of soluble cytokines, proinflammatory (and anti-inflammatory (cytokines by Luminex assay. At the end of the sample analysis, any remaining sample will be discarded.

8.2.4 Specimen Shipment

The analysis of the specimens will be performed by the Center for Innovative Biomedical Resources (CIBR core).

9 ASSESSMENT OF SAFETY

9.1 Specification of Safety Parameters

This study involves the use of Erenumab, a fully human monoclonal antibody that is a CGRP antagonist FDA approved for the management of chronic migraine.

The participants of this study will be closely monitored and follow up in their clinic visits and between visits with telephone calls. As part of the study outcomes, the study staff will record information regarding AEs. Overall health parameters will be captured on case report forms. These will be completed at every visit and data will be compiled for review by the IRB and AMGEN.

The description of potential risks is described in 2.3 and 6.3. The most common side effects of the use of Erenumab are:

Injection site reactions: which may include tenderness, pain, redness, itching,

bruising, firmness, or hypersensitivity

- Constipation
- Muscle spasms/Cramps
- Itching (pruritus)

Allergic reactions can happen within hours to days after using erenumab. Therefore, after the injection is administered, the participant will wait in the room for 20 minutes and the evening of the treatment visit, the participant will receive a follow up phone call and the information will be recorded.

9.1.1 Unanticipated Problems

The Office for Human Research Protections (OHRP) considers unanticipated problems involving risks to subjects or others to include, in general, any incident, experience, or outcome that meets **all** of the following criteria:

 unexpected in terms of nature, severity, or frequency given (a) the research procedures that are described in the protocol-related documents, such as the IRBapproved research protocol and informed consent document; and (b) the characteristics of the subject population being studied;

- - related or possibly related to participation in the research ("possibly related" means
 there is a reasonable possibility that the incident, experience, or outcome may
 have been caused by the procedures involved in the research); and
 - suggests that the research places subjects or others at a greater risk of harm (including physical, psychological, economic, or social harm) than was previously known or recognized.

9.1.2 Adverse Events

An adverse event is any untoward or unfavorable medical occurrence in a human subject, including any abnormal sign (for example, abnormal physical exam or laboratory finding), symptom, or disease, temporally associated with the subject's participation in the research, whether or not considered related to the subject's participation in the research.

9.1.3 Serious Adverse Events

A serious adverse event (SAE) is one that meets one or more of the following criteria:

- Results in death
- Is life-threatening (places the subject at immediate risk of death from the event as it occurred)
- Results in inpatient hospitalization or prolongation of existing hospitalization
- Results in a persistent or significant disability or incapacity
- Results in a congenital anomaly or birth defect
- An important medical event that may not result in death, be life threatening, or require hospitalization may be considered an SAE when, based upon appropriate medical judgment, the event may jeopardize the subject and may require medical or surgical intervention to prevent one of the outcomes listed in this definition.
- Severe allergic reactions due to Erenumab: Severe skin reactions, difficulty breathing or swallowing.
- Severe constipation that may need hospitalization.

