5.4.2 Masking Procedures (if applicable)

All study staff, including investigators, study care providers, study clinician, study coordinators, and research assistants, will remain blinded to the participants' medication assignments throughout the study. Erenumab and Placebo will be packaged in identical vials and stored. Only IDS, the research pharmacy will be unblinded. If the IRB and/or Data and Safety Monitoring Board (DSMB) request an unblinded data report during the data collection period, an unblinded biostatistician will generate the report.

Unmasking/unblinding prior to study completion will occur only if there is evidence that a participant's health or safety is threatened and therefore, knowledge of treatment assignment is necessary to protect the participant.

Except in extreme medical emergencies, before a participant's treatment assignment is revealed, the investigator must confer the request for unmasking with the IDS. For a medical emergency that occurs during business hours, the site investigator will contact the IDS to determine the participant's treatment assignment; for a medical emergency that occurs outside of business hours, medical personnel will contact the IDS pharmacy to determine the treatment assignment.

An event is considered an extreme medical emergency when medical management of a participant requires the knowledge of the treatment assignment. Study participants will be provided with instructions and contact information for emergency situations. Emergency unmasking will be recorded and reported to the PI, and the medical monitor as soon as possible, with a full accounting of the event, date and time of occurrence, the reason for unmasking, and names of all individuals who were notified of the emergency. Unblinding will be reported to the Data Safety Monitoring Board (DSMB) and IRB according to the University of Maryland policies and guidelines.

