6.2 Dosage, Preparation and Administration of Study Product

Erenumab 140 mg/mL or placebo prefilled glass syringe will be administered subcutaneously once monthly.

Erenumab or placebo will be administered by the study personnel who will be trained in how to administer it using the single-dose prefilled syringe, including aseptic technique and according to the instructions of the manufacturer.

• Prior to subcutaneous administration, allow Erenumab to sit at room temperature for at least 30 minutes protected from direct sunlight.

- - Do not warm by using a heat source such as hot water or a microwave.
 - Do not shake the product.
 - Inspect visually for particulate matter and discoloration prior to administration [see Dosage]
 - Do not use if the solution is cloudy or discolored or contains flakes or particles.
 - Erenumab or placebo will be administered in the abdomen, thigh, or upper arm subcutaneously.
 - It will not be injected into areas where the skin is tender, bruised, red, or hard.
 - Both prefilled autoinjector and prefilled syringe are single-dose and deliver the entire contents.
 - Erenumab or placebo administration to participants will be once a month for 3 months on Visits 1-3. The study personnel will explain the participant how it will be injected. Participants will receive the first dose on Visit 1. The second dose a month after on Visit 2 and the third and last dose a month after the second dose on Visit 3 for a total of 3 cycles. After administration, the patient will wait 20 minutes in our clinic to make sure there is not any reaction. After the 20 minutes, study personnel will assess, schedule next visit and the patient will be free to leave.
 - Erenumab or placebo is for subcutaneous use only. The needle shields of erenumab and placebo prefilled syringe contain dry natural rubber (a derivative of latex), which may cause allergic reactions in individuals sensitive to latex. Sensitivity to latex is included in the exclusion criteria (See 5.2)

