9.3 Characteristics of an Adverse Event

9.3.1 Relationship to Study Intervention

To assess relationship of an event to study intervention, the following guidelines are used:

- 1. Related (Possible, Probable, Definite)
 - a. The event is known to occur with the study intervention.
 - b. There is a temporal relationship between the intervention and event onset.
 - c. The event abates when the intervention is discontinued.
 - d. The event reappears upon a re-challenge with the intervention.
- 2. Not Related (Unlikely, Not Related)
 - a. There is no temporal relationship between the intervention and event onset.
 - b. An alternate etiology has been established.

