9.4.2 Serious Adverse Event Reporting to AMGEN Safety and UMB IRB

Any AE meeting the specified Serious Adverse Event criteria will be submitted on an SAE form to the IRB and AMGEN Safety.

The PI will complete a Serious Adverse Event Form and submit via fax or email within the following timelines:

- All deaths and immediately life-threatening events, whether related or unrelated, will be recorded on the Serious Adverse Event Form and submitted to Product Safety within 24 hours of site awareness.
- Serious adverse events other than death and immediately life-threatening events, regardless of relationship, will be reported by fax within 72 hours of site awareness.

All SAEs will be followed until resolution or stabilization.

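### The allergic-reaction SAE criterion in Section 9.1.3 requires attribution to erenumab, which blinded staff cannot establish, so some severe reactions become SAEs only by discretion

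*Combined protocol and SAP*

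**What the plan says.** Section 9.1.3 opens its definition with "A serious adverse event (SAE) is one that meets one or more of the following criteria". Eight criteria follow. Six are general: death, threat to life, hospitalisation, disability, birth defect and important medical event. Two are specific to this study. One is severe constipation that may lead to hospital care, with no cause named. The other is "Severe allergic reactions due to Erenumab: Severe skin reactions, difficulty breathing or swallowing".

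Section 9.4.2 sets two reporting clocks. Deaths and immediately life-threatening events go to the company within 24 hours, related or not. All other SAEs, "regardless of relationship, will be reported by fax within 72 hours of site awareness".

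Section 5.4.2 says that all study staff, investigators included, "will remain blinded to the participants' medication assignments throughout the study". Section 5.4.1 says the same of the PI and staff.

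Section 6.2 gives a cause of allergic reaction common to both arms: "The needle shields of erenumab and placebo prefilled syringe contain dry natural rubber (a derivative of latex), which may cause allergic reactions".

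Section 9.3.1 handles causality separately. It offers guidelines for calling an event related or not related to the study intervention.

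**The concern.** Seriousness should describe what happened to the participant. Cause is a separate judgment, and this protocol otherwise keeps the two apart: relatedness is graded in Section 9.3.1, and Section 9.4.2 reports SAEs whatever that grade. The allergic-reaction line breaks the separation. An event that fails the definition never reaches Section 9.4.2, so a causal filter at the definition step partly undoes the rule that relationship does not matter for reporting.

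The filter also names the active drug. Blinded staff can judge whether a reaction might be due to the injection, but they cannot know whether the injection contained erenumab. The protocol does not tell them to treat every participant as if on active drug when they apply this line. Two participants with the same reaction could therefore be classified differently, depending on what staff suspect.

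At stake are the consistency of the SAE count and prompt reporting of a small class of reactions. SAE numbers are among the events that Section 9.5 says might trigger a safety review.

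**Working it through.** The documents give no figure to reproduce here. The check traces a severe allergic reaction through the definition and then through the reporting rule.

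**Step 1: how the criteria combine.** Section 9.1.3 needs one criterion or more. The allergic-reaction line can add events to the SAE set and cannot remove any. The question is which severe reactions depend on it.

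**Step 2: routes to SAE status.**

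| Severe skin reaction, or difficulty breathing or swallowing | Attributed to erenumab | Attributed to something else |
|---|---|---|
| Fatal, life-threatening, hospitalised or disabling | SAE by a general criterion | SAE by a general criterion |
| None of these | SAE by the allergic-reaction line | SAE only if staff choose to use the important-medical-event criterion |

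The lower right cell is the gap. The important-medical-event criterion is permissive: it says such an event can be treated as an SAE on medical judgment, not that it must be. The study-specific line would make these reactions automatic SAEs, and the attribution takes that away for this cell.

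**Step 3: can the two columns be told apart under blinding?** Not by knowledge of the arm (Sections 5.4.1 and 5.4.2). A cause other than the drug is plausible on the protocol's own terms, since both needle shields contain the latex derivative described in Section 6.2. Exclusion criterion 18 in Section 5.2 removes patients sensitive to latex, which reduces this route but covers only those whose sensitivity is identified.

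**Step 4: consequence for reporting.** In the lower left cell the event falls under the 72-hour rule. In the lower right cell it does so only if discretion is used. Otherwise it is recorded as an AE outside Section 9.4.2.

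**Step 5: comparison with the neighbouring line.** The constipation criterion carries no attribution to the drug. The two study-specific lines are therefore built differently, and the allergic-reaction line can follow the other's form.

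**Step 6: size.** With 20 participants per arm, one event classified one way or the other changes an arm's SAE proportion by 1/20 = 5 percentage points, and the proportion in the whole trial by 1/40 = 2.5 points. This is the effect of one event, not an estimate of how often it will happen. The documents give no rate for severe allergic reactions; Section 9.3.2 lists them only as post-marketing reports.

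**The case against.** The strongest reply is that little is lost. The line only adds to the list, and serious difficulty breathing or swallowing will often count as life-threatening or as an important medical event. Blinded investigators judge suspected causality routinely, and nothing tells them to presume placebo. All AEs are recorded whether or not related (Section 9.1.2) and graded by CTCAE (Section 9.3.3). A participant who reports hypersensitivity is discontinued (Section 6.3) with the reason recorded (Section 5.5.2). The review triggers in Section 9.5 include the number and type of severe AEs, so such a reaction can prompt review without the SAE label. Safety is summarised descriptively (Section 12.3), with no comparative SAE test to distort. All of this stands. It limits the severity but does not close the lower right cell of the table.

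A reader might also infer three stronger points that the documents do not support:

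- **That a severe allergic reaction is an SAE only if due to erenumab.** The list needs any one criterion, and the general criteria carry no causal condition.
- **That the relatedness list in Section 9.3.1 lets SAEs escape expedited reporting.** Once an event is an SAE, Section 9.4.2 ignores relationship.
- **That almost no event could be both related and unexpected, because one relatedness item asks for prior knowledge.** Section 9.1.1 counts an event as "unexpected in terms of nature, severity, or frequency", so a known event can still be unexpected in severity or frequency. That section also has its own test of possible relatedness, a reasonable possibility.

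Section 9.3.1 does lack a rule for combining its items. One of them, "The event reappears upon a re-challenge with the intervention", cannot be observed after a hypersensitivity reaction, because the participant is discontinued. But the items are called guidelines, and the text states neither an all-items nor an any-item test. This is missing detail, not a contradiction.

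**Conclusion.** The point holds for the one line in Section 9.1.3. It mixes cause with seriousness, names the active drug in a blinded trial, and fits badly with reporting regardless of relationship in Section 9.4.2. As a result, severe allergic reactions that meet no other mandatory criterion and are attributed elsewhere depend on discretion for SAE status and for the 72-hour clock.

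The severity is low. Few events are expected among 40 participants, most grave reactions qualify by another route, and severe AEs remain visible to safety review. The conclusion assumes that the line is applied as worded and that no other rule makes these reactions SAEs. Section 9.4.5 mentions a Table 2 in Section 9.4.2, and Section 9.4.1 contains figures. Neither was legible in the copy examined, and either may add reporting rules.

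**What to change.** In Section 9.1.3, delete the attribution to erenumab, so that the line covers severe allergic reactions (severe skin reactions, difficulty breathing or swallowing) after any study injection, whatever the suspected cause. Leave the causal judgment to Section 9.3.1.

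As a secondary clarification, align Section 9.3.1 with the reasonable-possibility standard already in Section 9.1.1, so that prior knowledge, abatement and re-challenge serve only to raise the grade from possible to probable or definite.

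The cost is about two sentences in a protocol amendment. Slightly more events may be reported as SAEs or graded as related. No analysis or sample size changes.
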